**In-Hospital Follow-ups.** These assessments will be conducted 2-3 days and 3-5 days after the baseline assessment, during the course of hospitalization. If patients are discharged during this time, only the first follow-up will be obtained. Participants will be asked to complete a "modified" SI that assesses suicidal ideation over the past 48 hours to assess recent change , Contemplation Ladders and the PDM. When it is time to conduct the in-hospital follow-up assessment, a researcher on the unit will call a researcher at the CoE who will conduct the assessment by telephone. This will ensure that outcome assessments are conducted by researchers who are blind to condition.

**Post-Discharge Follow-ups.** Follow-up assessments will be conducted at 1, 3, and 6 months via telephone. A telephone follow-up will enable us to expand the catchment area and assess

participants who are hospitalized or in residential treatment and unable to return to the medical center. Procedures will include mailing participants the assessment measures to ease administration. There is precedence for this strategy, as the telephone administered SSI was the primary outcome for the PROSPECT trial, supporting use of the method.  In addition to the SSI, we will also use all risk-factors measures that are used at baseline including the PHQ-9, PCL-C, BAI, AUDIT, DAST-10, SUF, InDUC, ISI, C-SSRS, Contemplation Ladders, HCCQ, TSRQ, PCQ, PDM as well as the exploratory outcome measure the TSR-6 (Table 3). The window for each assessment will open at the midpoint between the previous assessment and the current assessment, and close at the midpoint between the current assessment and the following assessment (e.g., open two weeks before month 1 and close at the end of month 2, the midpoint between 1 and 3 month assessments), and close 3 months after the 6-month follow-up.

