Chart Reviews. Research assistants will review participants' charts at two points during the study. The baseline chart review will take place after the baseline interview. Research assistants will cull treatment data from VA medical records using a protocol that we have used in a previous study. Center staff has received 8 hours of training in the protocol and achieved inter-rater reliability as part of the previous study. The protocol emphasizes suicidality, service engagement in the past year, services received during the visit prior to hospitalization, and risk factors for suicide such as depression and substance use disorders. Follow-up chart reviews will occur in concordance with the 6-month follow-up assessment. The protocol will be an abbreviated version of baseline protocol, with the time period limited to the 6 months following discharge. The chart review will also be used to assess use of VA suicide prevention services including the Safety Plan, SPCs, High-risk List, and case managers so that we can describe TAU components that participants receive. Center research assistants already trained in the chart review protocol that will be used. If additional assistants need training, we will use the existing training protocol, which consists of 8 hours of training in the protocol and reviewing practice charts.

**Research Assistant Training and Supervision.** Research assistants will conduct all assessments and receive detailed training and supervision to ensure standardization.

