Primary Analysis 1: An over-dispersion Poisson generalized linear mixed model (GLMM) with maximum likelihood estimation will be used to examine the effect of MI-SI on the severity of SI at 1, 3, and 6 months follow-up. GLMM was chosen because random effects are added to the model to account for repeated measures within subjects. An over-dispersion Poisson GLMM will be used because the SSI is bounded at zero and had a standard deviation larger than the mean at follow-up in our pilot data, indicating over-dispersion. If data do not meet the assumptions of a Poisson distribution, we will use a negative binomial or zero-inflated negative binomial. The benefit of using maximum likelihood estimation is that it yields unbiased estimates in the presence of missing data, if data are missing at random. Because participants may receive one or two sessions of MI-SI, and the change pattern may not be linear over time, we will test sessions of MI-SI, time of assessment, and their interaction in follow-up analyses. As an added measure of clinical significance, we will report the number of participants in each group who fall below the two-point cut-off.

Because the presence of any suicidal behavior (i.e., attempted suicide, interrupted attempts, preparatory behavior) is an important outcome, we will use a mixed effects general logistic model to examine the effect size of MI-SI on the incidence of suicidal behavior as measured by the C-SSRS over follow-up assessments.

Exploratory Hypothesis 1: Participants who receive MI-SI plus TAU will engage in more treatment over follow-up than participants who receive TAU alone.

Exploratory Analysis 1: Multivariable logistic regression will be used to examine the effect of MI-SI on treatment engagement. The Hosmer-Lemeshow statistic will be used to evaluate model fit, and odds ratios with 95% confidence intervals will be derived using the method of maximum likelihood.  Because participants may receive one or two sessions of MI-SI, we will conduct a sensitivity analysis examining the number of MI-SI sessions as a predictor of treatment engagement. Because this is an underpowered exploratory analysis, we will also conduct secondary analyses using other definitions of treatment engagement such as number of sessions attended.

We will also examine the impact of the intervention on use of the Safety Plan coping strategies. To test treatment differences, we will use a multivariable logistic regression.

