#### Warm Transfer Process

- 1. Press the **conference** button.
- 2. Dial [name] press option 1 and a Crisis Line responder will answer.
- 3. Describe the participants risk and provide name and telephone number.
- 4. Pressing the **conference** button and participants will be linked with Crisis Line counselors.

It is possible that participants may refuse to be transferred to the Crisis Line or hang up. As a result, research clinicians will ask participants to use a landline for MI-SI telephone sessions so that the number can be tracked to an address if emergency services are needed. For participants who only have a cell phone, interviewers will begin each session by asking the participant for the address from which they are calling so that the clinician can send help if it is needed. Because participants may give a false address, clinicians will consult with Crisis Line responders who have a protocol for emergency responses for cell phone callers.

Adverse Events (AE). All suicide attempts and episodes of imminent risk that require intervention will be considered adverse events and will be addressed according to IRB regulations. The determination of an AE will be made by an investigator other than the PI (i.e., [name] or [name]), to reduce the possibility of bias. Syracuse VA IRB also requires that serious adverse events, any event leading to a deviation from the protocol such as emergency hospitalization (e.g., to address acute suicidality) or death, be reported to the principal investigator within 24 hours, who is required to report them to the IRB within 48 hours. Adverse events that are minor such as temporary distress will be recorded by interviewers and reported to the IRB annually. All adverse events will be reported to the principal investigator within 24 hours to establish the level of significance and determine the appropriate procedure.

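### The suicidal-behavior outcome does not count suicide death and rests on C-SSRS telephone interviews alone, although chart-review and adverse-event records of such events are already planned

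*Combined protocol and SAP*

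**What the plan says.** In the Combined protocol and SAP, Primary Analysis 1 (Analytical Plan) adds a mixed-effects logistic model to the SSI analysis. The reason given is that "the presence of any suicidal behavior (i.e., attempted suicide, interrupted attempts, preparatory behavior) is an important outcome". The model estimates the effect size of MI-SI on "the incidence of suicidal behavior as measured by the C-SSRS over follow-up assessments". The parenthetical list follows an i.e., so it reads as the definition, and suicide death is not in it.

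After discharge the C-SSRS is part of a participant interview: "Follow-up assessments will be conducted at 1, 3, and 6 months via telephone" (General Procedures, Post-Discharge Follow-ups).

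Two other planned records bear on the same events:

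- **Chart review.** "Follow-up chart reviews will occur in concordance with the 6-month follow-up assessment" and cover the 6 months after discharge. They use an abbreviated form of the baseline protocol, of which the section says "The protocol emphasizes suicidality, service engagement in the past year". The stated purposes are treatment data and description of usual care: "The chart review will also be used to assess use of VA suicide prevention services".
- **Adverse events.** "All suicide attempts and episodes of imminent risk that require intervention will be considered adverse events". Serious adverse events include "any event leading to a deviation from the protocol such as emergency hospitalization (e.g., to address acute suicidality) or death" and go to the IRB. The Data Monitoring Committee section sends them to the DMC as they occur.

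No section links either record to the suicidal-behavior analysis. Missing data are handled in general terms: all available data, multiple imputation where appropriate (Data Preparation), and a missing-at-random argument made for the SSI model (Primary Analysis 1).

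**The concern.** A participant who has died cannot be interviewed, and one who has attempted suicide may be harder to reach. An interview-only outcome is therefore likely to be missing for reasons tied to the outcome itself. Likelihood estimation and imputation help only if data are missing at random. They also do not make a known death count as an event, and they would leave an attempt already written in the chart to be imputed.

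The analysis is secondary to the SSI, but it carries weight. The Specific Aims say this trial sets the stage for a trial on suicidal behavior, and the Power Analysis section foresees possible concern about harm. A randomised comparison that leaves out the most severe event, and attempts the trial knows about, is weaker for both uses than the planned records allow.

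**Working it through.** **Plan's own figures.** The Power Analysis section states 112 participants and 80% retention. 112 × 0.80 = 89.6, which matches its 90 with 6-month data. The stated power values also reproduce. The change-score variance factor is (1 + 2 × 0.70)/3 + 1 − 2 × 0.50 = 0.80 and the effective SD is 8.4 × √0.80 = 7.51. With 45 per arm, one-sided power is 0.935, 0.811 and 0.598 for 5, 4 and 3 points, against the stated 0.94, 0.81 and 0.60. These values concern the SSI. No power is stated for suicidal behavior, so there is no figure to correct.

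**Participants without a 6-month interview.** 112 − 90 = 22, or 22/112 = 19.6%.

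**Participants with events among those 22.** The documents give no 6-month incidence. Assume 10% to 25%, with equal risk in those reached and not reached:

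- 22 × 0.10 = 2.2
- 22 × 0.25 = 5.5

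This gives about 2-6, and it is an upper figure at equal risk because it treats all 22 as never interviewed. Suppose instead that non-response is 10%, 15% and 20% at 1, 3 and 6 months, that risk is uniform over time, and that each interview covers only the period since the one before (all assumptions). The unseen share is then 0.10 × 1/6 + 0.15 × 2/6 + 0.20 × 3/6 = 0.167. That gives 112 × 0.10 × 0.167 = 1.9 to 112 × 0.25 × 0.167 = 4.7. The C-SSRS look-back at follow-up is not stated. If a later interview reaches back over a missed one, fewer are lost.

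**What can be recovered.** These counts include interrupted attempts and preparatory behavior. Adverse-event records are stated to hold attempts and deaths, and the follow-up chart items are not specified. The recoverable number is therefore smaller, and the documents do not allow it to be calculated.

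**Expected suicides.** Background and Significance cites 445 per 100,000 in the year after discharge.

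- Full-year rate: 112 × 0.00445 = 0.50
- Half of it: 0.25

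The same section says 46% of those deaths fell within 3 months, and 0.46 × 0.50 = 0.23. The 6-month figure therefore plausibly lies between 0.25 and 0.5. The other cited rate, 568 per 100,000 in 12 weeks, gives 112 × 0.00568 = 0.64 if it is a 12-week risk. The text does not say whether it is annualised.

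**The case against.** The case against making much of this is substantial.

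- **Loss is already reduced.** Telephone follow-up was chosen partly to reach people who are in hospital or residential care. The windows are wide and there are 14 tracking procedures. This lowers the number missed but does nothing for deaths.
- **The list may be loosely worded.** The i.e. might have been meant as examples. Even so, the named source is an interview with the participant, which cannot record that participant's death.
- **Oversight is intact.** A reader might infer that deaths and attempts vanish from the trial. They do not: known events go to the IRB and serious ones to the DMC. They are absent only from the randomised comparison.
- **A composite could add bias.** A reader might infer that a chart-supplemented composite should replace the C-SSRS outcome. The documents do not support that. Only MI-SI participants receive the booster call, and MI-SI is expected to raise treatment engagement, so attempts may be detected more often in that arm. MI-SI session notes are entered in the medical record, so a chart reviewer can see assignment, whereas follow-up interviewers are blind. A composite that scores an unreached person with an empty chart as event-free would turn missing data into an assumed negative.
- **The records may be incomplete.** The follow-up chart form is abbreviated. The text does not say whether it keeps attempts, or whether it is completed for people who miss the 6-month interview.

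The last two points stand and shape the fix. None of them explains why a known suicide should not count as an event.

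**Conclusion.** The point holds at moderate weight. The definition omits suicide death, and the only source is an interview that the deceased and the unreached cannot give. The supplementary records are planned but unused for this outcome. At most about 2-6 participants with events are unseen at equal risk, given 80% retention and an assumed 10-25% incidence. Earlier interviews reduce that number, and only part of it is recoverable. Expected suicides are about 0.25-0.5. The primary SSI analysis and all stated power values are unaffected.

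Two larger claims should not be drawn:

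- **A count of 4-11 unseen events.** This needs double the risk in those lost (22 × 0.20 = 4.4; 22 × 0.50 = 11). That is plausible, but the documents give no figure for it. The pilot's 61.5% with a prior attempt is the history of 8 of 13 people, not a 6-month incidence.
- **A treatment effect biased in a known direction.** Take no true effect, 15% incidence in each arm, three times the risk in those lost, and 85% v 75% retention. The risks among those reached are 0.15/(0.85 + 3 × 0.15) = 0.115 and 0.15/(0.75 + 3 × 0.25) = 0.100, an odds ratio of 1.17. With 80% retention in both arms it is 1.00. The plan gives no retention by arm, so this shows only that bias is possible.

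**What to change.** 1. **Main definition.** Count suicide death within 6 months of discharge as an event alongside the listed C-SSRS behaviors, for everyone randomised. State how a death enters the repeated-measures model, for example in the assessment interval in which it occurs.
2. **Sensitivity analysis.** Also count attempts documented in the 6-month chart review or the adverse-event records within the same fixed 6 months. The fixed period matters because the last interview window closes 3 months after the 6-month point, while the chart review covers only 6 months.
3. **Safeguards.** Run the same search in both arms, including participants who miss the 6-month interview. Classify events from extracts that hide study assignment. Do not treat an unreached participant with no chart entry as a confirmed non-event.

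The cost is SAP wording, a check that the abbreviated chart form captures attempts and deaths, preparation of masked extracts, and a merge of records already planned. The small downside is uneven detection: charts mainly cover VA care, and the booster call may raise detection in the MI-SI arm. That is why the supplemented outcome belongs in a sensitivity analysis.

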- 6. TBI (7 items): The Ohio State TBI-ID short form is a valid and reliable screen for TBI. TBI-related dementia will be identified by positive screen for moderate to severe TBI and a score of 26 or lower on the MMSE, the conservative cutoff point for the MMSE. 
- 7. Suicidal Ideation (SI): SI will be measured with the Scale for Suicidal Ideation (SSI)  $^{27}$ . The SSI is an interview that measures the "intensity of the patient's specific attitudes, behaviors, and plans to commit suicide" (p. 4).  $^{44}$  Participants will be asked about "current" suicidal ideation defined as occurring during the past week (SSI-C),suicidal ideation at its "worst point" in the patient's life (SSI-W) at baseline, and "acute" suicidal ideation in the last 48 hours. The SSI is considered the gold standard measure for SI, has been found to have good internal consistency ( $\alpha = 0.84$ ), construct validity,  $^{52}$  and predictive validity as scores over 2 are predictive of suicide,  $^{3}$  and has been used with Veterans.  $^{53}$  The SSI-C will be used to measure SI the week prior to admission to obtain an accurate measure of SI during the period of acute risk that preceded hospitalization, and to avoid underestimating the severity of SI due to the benefits of hospitalization. The SSI-C is sensitive to change over time in adult clinical samples and will also be used to assess the severity of SI at follow-up assessments.  $^{3}$

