- 7. Drug Use Consequences (15 items): The Inventory of Drug Use Consequences (INDUC)  $^{67}$  is the gold-standard self-report assessment of substance-related consequences in the past 90 days. It has been used with Veterans.  $^{68}$
- 8. Insomnia (7 items): The Insomnia Severity Index (ISI) is a widely used, reliable and valid self-report instrument of sleep difficulty. 
- 9. Anger (5 items): The Lifetime History of Aggression Questionnaire (LHAQ) is a brief, valid, and reliable measure of aggression .
- 10. Treatment Engagement (26 items): Treatment engagement will be measured using the Alcohol and Drug Services, Medication, Medical Services, and Psychological Services sections of the Treatment Services Review (TSR-6) which have been shown to be both reliable and valid. 71 The TSR-6 will be used at baseline and the 1, 3 and 6 month follow-ups to inquire about use of these services. The baseline assessment will be used to compare engagement in psychological and alcohol and drug service use between groups to assess whether it needs to be accounted for in the analyses. Engagement in psychological and alcohol and drug services will also be assessed at each follow-up assessment and used as an exploratory outcome. Treatment engagement will be treated as a dichotomous outcome, and will be defined according to the Substance Abuse and Mental Health Services Administration (SAHMSA) Washington's Circle standards, 72 which have been adopted by VA. 73 For residential patients and inpatients, treatment engagement is defined as attending two outpatient visits in the 30-days after discharge. In Veterans with substance use disorders, this measure of treatment engagement has been found to be associated with treatment outcome 74 and hospitalization in those with a suicide attempt history. 75 In Veterans discharged from psychiatric hospitalization, completing two outpatient sessions in at least two of the six months after discharge has also been found to be associated with suicide. 1
- 11. Suicidal Behavior (18 items): The Colombia Suicide Severity Rating Scale (C-SSRS)  will be used to assess history of suicidal behavior at baseline and at follow-up assessment. It has been mandated for use in medication trials by the FDA. 

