In session 1, clinicians will attempt to proceed through all three phases. In session 2, clinicians will summarize session one and use patients' response to the summary to decide which phase to return to. If patients are in phase 3, clinicians' will help them refine and reinforce their plan. If they are undecided about mental health or substance abuse treatment, clinicians will return to phases 1 or 2 and explore reasons against engaging in treatment, build the motivation to engage in it, and strengthen their commitment to do so. Veterans in the MI-SI condition will also complete one telephone booster MI-SI session (30-50 mins.) within one-month (weeks 3-6) after discharge. Telephone contact within one month after discharge is a component of treatments that have been found to reduce risk for suicidal behavior and will be used to increase the dosage of MI-SI.  Participants will be provided a handout with the scheduled telephone follow-up and therapist contact information. Telephone sessions will consist of an abbreviated MI-SI interview following the strategy of session 2. For telephone sessions, phase 3 will include a review of their mental health and substance abuse treatment and explore alternative or additional treatments if they are called for. All MI-SI sessions will also be recorded for coding.

TAU. All patients that are admitted to the acute psychiatric unit receive standard inpatient treatment that includes medication management, case management, meals and a bed, and milieu therapy consisting of creative and social activities (e.g., crafts, video games, karaoke). Families of Veterans may also receive education concerning the Veteran's problems to create a supportive home environment. Suicidal patients receive additional services. VA mental health clinicians are required to complete a Safety Plan with all suicidal Veterans, and each VAMC has hired a Suicide Prevention Coordinator (SPC) to oversee the care of high-risk patients. The Syracuse VAMC also hired Case Managers to help meet essential living needs of suicidal Veterans. SPCs and Case Managers work collaboratively to help suicidal patients transition from inpatient to outpatient treatment. Chart reviews will provide a detailed description of the components of TAU that each participant receives so that suicide-specific TAU can be described in detail. Suicide-related TAU will be controlled for in analyses if differences are observed between conditions.

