Exploratory Hypothesis 2: Treatment engagement over follow-up will partially mediate the impact of MI-SI on SI.

Exploratory Analysis 2: Analyses will examine treatment engagement as a mediator of the impact of MI-SI plus TAU on SI. Treatment engagement is expected to partially mediate the relationship between randomization to the MI-SI group and SI over follow-up, such that the relationship is smaller but the effect size is still significant. Structural equation modeling (SEM) will be used to examine this potential mediation relationship. SEM is a method for creating latent

variables and identifying and describing causal relationships between the latent variables. We decided to use SEM because it simultaneously tests independent and conjoint relationships and uses latent variables, which minimizes measurement error. The model will consist of both latent and observed variables. Latent variables will be used for variables such as SI (via the SSI) to fit the data for this population. Observed variables will be used for variables such as randomization to MI-SI and treatment engagement (via the TSR). Because these analyses will be underpowered, this exploration will be based on effect sizes rather than statistical significance. Furthermore, we will also conduct more basic mediation regression models as secondary analyses.

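### Exploratory Analysis 2 pairs 30-day engagement with SI that includes the overlapping 1-month SSI, without a stated time order or adjustment for earlier SI, so the indirect effect can be biased in the hypothesised direction

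*Combined protocol and SAP*

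**What the plan says.** - **Hypothesis and model.** Exploratory Hypothesis 2 reads "Treatment engagement over follow-up will partially mediate the impact of MI-SI on SI". Exploratory Analysis 2 repeats that "Treatment engagement is expected to partially mediate the relationship between randomization to the MI-SI group and SI over follow-up". It plans a structural equation model with randomization and engagement as observed variables and SI as latent, plus simpler mediation regressions as secondary analyses. Because the analysis is underpowered, it is to be read from effect sizes, not significance.
- **Mediator.** Under Baseline Assessment, item 10, "treatment engagement is defined as attending two outpatient visits in the 30-days after discharge". It is a yes/no variable. "The TSR-6 will be used at baseline and the 1, 3 and 6 month follow-ups", which are also the contacts at which the SSI is taken.
- **Outcome.** The primary analysis defines the follow-up times: it examines "the effect of MI-SI on the severity of SI at 1, 3, and 6 months follow-up". The follow-up SSI asks about the past week (Screening Assessment, item 7).
- **Assessment window.** Under Post-Discharge Follow-ups, the 1-month window can "open two weeks before month 1 and close at the end of month 2".
- **Not stated.** Exploratory Analysis 2 gives no lag, does not say which engagement report goes with which SSI score, and names no adjustment for earlier SI. Data Preparation provides for covariates when the arms differ at baseline, which is a different matter.

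**The concern.** A mediator should be settled before the outcome it is meant to explain. Here the 1-month SSI can describe the same days in which engagement is still accruing, so an association between the two cannot separate engagement lowering SI from SI determining who attends.

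The second direction is the protocol's own theory. Background and Significance argues that Veterans in whom the wish to die dominates may decline treatment, and that those with a stronger wish to live may take it up.

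The effect size is the sole basis for judging this hypothesis, and the fault is a bias in that effect size. Neither a significance threshold nor a larger sample would guard against it. The trial is also meant to inform later work on how MI-SI operates.

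**Working it through.** **1. Timing.** The engagement window is days 0 to 30 after discharge. The 1-month contact can fall from about day 15 to about day 60. Taken on time, its past-week SSI covers about days 23 to 30, inside the window. Taken at the opening, it covers about days 8 to 15. Only a late contact falls wholly after the window. The 3- and 6-month scores follow it. If engagement over follow-up instead means engagement to 6 months, the overlap reaches all three SSI scores.

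**2. The plan's inputs reproduce its own power figures.** Power Analysis gives SD 8.4, correlation .50 between baseline and follow-up, .70 between follow-ups, and 45 per arm.
- Variance factor for change: (1 + 2 × 0.70)/3 + 1 − 2 × 0.50 = 0.80. SD = 8.4 × √0.80 = 7.513.
- One-sided power for 5, 4 and 3 points: .935, .811, .598 (stated .94, .81, .60).
- Two-sided power: .884, .714, .474 (stated .88, .71, .47).

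**3. Direction of the bias.** Let MI-SI shift SI by τ, and let SI shift the log odds of engagement by γ per SD. Suppose engagement has no effect on SI. The arm-to-engagement path *a* has the sign of γτ, and the engagement-to-SI path *b* has the sign of γ. The product *ab* therefore has the sign of γ²τ, which is the sign of τ. If τ = 0, then *a* = 0 and *ab* = 0.

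**4. Size.** I simulated large samples with τ = −4, 50% engagement, engagement driven by 1-month SI, and no effect of engagement on SI. The odds ratios and the engagement rate are assumptions. Linear models, *ab* in SSI points:

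| Model | OR 0.5 per SD | OR 0.33 per SD |
|---|---|---|
| Mean of 1, 3, 6 months, unadjusted | −0.31 | −0.62 |
| Mean of 1, 3, 6 months, baseline SSI adjusted | −0.22 | −0.45 |
| 3 and 6 months, baseline adjusted | −0.18 | −0.37 |
| 3 and 6 months, baseline and in-hospital SSI adjusted | −0.08 | −0.15 |
| 3 and 6 months, baseline and 1-month SSI adjusted | 0.00 | 0.00 |

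As shares of the 4-point effect, row 2 is 0.22/4 = 5.5% and 0.45/4 = 11%. A weaker assumed range (γ from −0.25 to −1.0, baseline adjusted) gives −0.03 to −0.39, or 0.8% to 9.7%. Using 64% engagement changes little (−0.11 against −0.12 at γ = −0.5).

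**5. Arithmetic check on the rows.** In units of the variance and given baseline, the 1-month SSI has variance 1 − 0.50² = 0.75, and covariance 0.70 − 0.50² = 0.45 with each later score.
- Its covariance with the three-score mean is (0.75 + 0.45 + 0.45)/3 = 0.55. Dropping the 1-month score scales the bias by 0.45/0.55 = 0.82: 0.22 × 0.82 = 0.18, and 0.45 × 0.82 = 0.37.
- The in-hospital row assumes that this score correlates .70 with later SSI and .50 with baseline; neither figure is in the documents. Conditioning on it leaves 0.45 − 0.45²/0.75 = 0.18, a factor of 0.18/0.45 = 0.4: about 0.07 and 0.15. At .50 with later SSI, it leaves 0.45 − 0.25²/0.75 = 0.37, a factor of 0.81: about 0.15 and 0.30. The gain depends on that correlation.

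**6. What each model does to a true effect.** Now let engagement truly lower SSI by 4 points at every follow-up, with MI-SI raising engagement (assumed odds ratio 2.7) and no reverse path. The true *ab* is about −0.98. The 3- and 6-month model with baseline adjusted recovers it, and so does the model that adds the in-hospital SSI. Adding the 1-month SSI cuts it to about −0.40. The arithmetic agrees: the slope of later on 1-month SSI given baseline is 0.45/0.75 = 0.60, so 40% of the effect survives, and 0.40 × 0.98 = 0.39.

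**The case against.** - **Low stakes.** The plan calls this analysis exploratory and underpowered. In simulated trials of 90, the sampling SD of *ab* is 0.34 to 0.49, as large as or larger than most of the bias. This stands and limits the weight of the point. It does not dispose of it: with τ = −4 and no true mediation, *ab* falls in the hypothesised direction in 68% (γ = −0.5) to 83% (γ = −1.0) of such trials, against 50% when MI-SI has no effect on SI.
- **Under-specified, not wrong.** A lagged model is compatible with the text. This is fair: the documents do not commit to a concurrent pairing at every visit. But the wording taken at face value includes the 1-month SSI, and nothing excludes it.
- **Reverse causation by itself.** A reader might infer that SI driving attendance is enough to create the artefact. It is not; MI-SI must also lower SI by a route other than engagement. Partial mediation presupposes such a route, so the condition is the plan's own premise.
- **Either direction would mislead.** A reader might also infer that the result would pass as support whichever way SI affects attendance. The product does keep its sign. But if higher SI raised attendance, MI-SI would appear to reduce engagement, against Exploratory Hypothesis 1, and both component paths would have the wrong sign, which the planned model would show.
- **Adjust for the 1-month SSI.** This looks like the complete remedy because it brings the bias to zero. Step 6 shows why it cannot be the main model: that score can lie on the path from engagement to later SI.

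**Conclusion.** The point holds as a matter of time order and unaddressed confounding by early SI. As written, Exploratory Analysis 2 can report an indirect effect in the hypothesised direction when engagement does nothing to SI. The size is modest: about −0.2 to −0.45 SSI points with baseline SSI adjusted, and about −0.3 to −0.6 without.

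This rests on a 4-point MI-SI effect, linear models, about 50% engagement, and odds ratios of 0.5 to 0.33 that are assumed and not taken from the documents. Moving the outcome to 3 and 6 months restores the order but does not by itself remove the bias, because early and later SI are correlated. If attendance is driven by early SI distinct from the 1-month score, that step alone changes nothing (about −0.10 either way at γ = −0.5).

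The documents do not support extending this to the primary analysis: sample size, power and significance level are unaffected.

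**What to change.** In Exploratory Analysis 2:
- State that the mediator is engagement in the 30 days after discharge, and reconcile this with the hypothesis wording about engagement over follow-up.
- Use the 3- and 6-month SSI as the outcome.
- Adjust for SI measured before engagement: the baseline SSI and the in-hospital 48-hour SSI. State which in-hospital score is used, since some participants will have only the first. That score comes after randomization, so put it in the outcome equation and not in the arm-to-engagement equation.
- If engagement reported at 3 months is also used, pair it only with the 6-month SSI.
- Apply the same order in the secondary mediation regressions.
- Report a model that also adjusts for the 1-month SSI as a sensitivity analysis only, and say that it can remove most of a true indirect effect.

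The cost is a change of wording; all these measures are already collected. Precision falls slightly, some bias remains if SI after discharge drives attendance, and mediation of the 1-month SSI is no longer assessed.
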